6.1.2 Descriptive analyses

The raw percent predicted FVC values and other spirometric endpoints will be listed by treatment, subject and visit/time. Descriptive statistics of both the raw and change in percent predicted FVC will be provided by treatment and visit/time. Summary statistics will include arithmetic mean, SD, CV (arithmetic), median, minimum and maximum.

Boxplots to visualize trends in spirometry endpoints will be created.

6.1.3 Statistical model, assumptions and hypotheses

The change from baseline in percent predicted FVC will be analyzed using a Bayesian model for repeated measurements including data collected at weeks 4, 8, 12 and 16. The model will investigate effects for treatment by time (included as a class variable) interaction, baseline percent predicted FVC by time interaction and will include the covariates prior sarcoidosis immunosuppressant therapy (stratification factor) and baseline prednisone dose. Uninformative priors for all the parameters will be utilized to obtain the posterior estimates. The correlation among the repeated measures collected on the same subject will be assessed via unstructured covariance matrix. The stratification factor may be removed in case of strata with low sample sizes impacting on the model fit. Baseline FVC and prednisone will be centered and standardized before used in the model

Commercially Confidential Information

6.1.3.1 Handling of missing values/censoring/discontinuations

The primary analysis will include all available information in terms of measurements at all times. If missing measurements are missing at random (MAR), an analysis of the available data provides consistent estimates of model parameters. Alternative assumptions may be explored to investigate the robustness of the results under plausible non-missing at random situations.

6.1.3.2 Graphical presentation of results

Posterior means with error bars (SD of the posterior) by treatment and time will be used to visualize the results over time.

6.1.4 Supportive analyses

If data permits, a subgroup analysis will be performed on the primary endpoint for the following two subgroups: subjects with a final prednisolone dose of 2.5 mg, subjects with a final prednisolone dose > 2.5 mg. The same analysis as defined in Section 6.1.3 will be performed, for each group.

Summary tables will be provided by subgroup.

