## 2.2 Secondary objective(s)

Secondary objective(s)	Endpoints related to secondary objective(s)

 
To assess the impact of CMK389 on steroid use (mg days)
 
	
 
Difference in steroid usage for each arm of the study between baseline and end of treatment
 

 
To assess the impact of CMK389 on a composite index of pulmonary physiology and exercise capacity
 
	
 
Proportion of patients who deteriorate from baseline to Week 16, defined as: relative reduction in FVC ≥ 10% or relative reduction in FEV1 ≥ 10% or relative reduction of DLCO ≥ 15% or relative reduction of 6MWD ≥ 50 m
 

Secondary objective(s)	Endpoints related to secondary objective(s)

 
To explore the impact of CMK389 observed with [F]-fluorodeoxyglucose positron emission tomography/computed tomography ([F]-FDG-PET/CT) imaging
 
	
 
Change in [F]-FDG-PET/CT (SUVmax and SUVmean) from baseline and Week 16
 

 
To assess the pharmacokinetics of

	
 
Pharmacokinetic parameters (Cmax/End of

CMK389	infusion, Ctrough) of CMK389

 
To assess the safety and tolerability of

	
 
Adverse events, vital signs and routine safety

CMK389	laboratory results.

 
To assess the impact of CMK389 on pulmonary physiology
 
	• Change in forced expiratory volume in one second (FEV1) and diffusion capacity for carbon monoxide (DLCO) between baseline and Week 16

 
To assess the impact of CMK389 on

	
 
Change in 6-minute walk distance (6MWD)

exercise capacity	between baseline and Week 16

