### Treatment Epoch

A 16-week treatment epoch will commence on Day 1. Patients with a CSD of "deteriorating" at this visit will be ineligible to continue in the study. Patients with a CSD of "improved" or "stable" will decrease steroid dose by 1-step. (Note: Steroids will not be tapered below 2.5 mg/day) Then, the patients will be randomized to receive CMK389 or placebo, stratified by prior sarcoidosis immunosuppressant therapy (Stratum 1: azathioprine or Stratum 2: methotrexate).

During the treatment epoch, steroid dose will be guided by the results of CSE/CSD (Figure 3-3). During the treatment epoch, adverse events will be monitored on an ongoing basis. Monthly visits are scheduled to assess safety and efficacy. Physical exam, vital signs, blood draw (safety labs, pharmacokinetic [PK] samples, CCI ), spirometry, 6MWT, mMRC and CCI will be performed during the treatment epoch every 4 weeks or as described in the Assessment Schedule (Table 8-1).

Every effort should be put in place to adhere to this algorithm, but in cases where the Investigator feels that, during the Treatment Epoch, a subject's increase in steroids outside of the specified incremental dose-steps indicated or re-initiation of methotrexate or azathioprine is clinically indicated, this therapy can be started/adjusted. All the actual treatments should be reported in the CRF and all the PD parameters collected after therapy adjustment will be excluded from the primary analysis.

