### Page 58 Protocol No. CCMK389X2201

Confidential

Novartis	Confidential
Amended Protocol Version v08 (Clean)	

Page 59
Protocol No. CCMK389X2201

Epoch	Pregnancy Testing Period (WOCBP Only) 				
Visit Name	Pregnancy Testing (WOCBP Only)	End of Study #2			
Visit Numbers 	401	499			
Days	225 ±3	253 ±3			
Pregnancy and assessments of fertility	S 	S 			
Serious Adverse Event - Only Pregnancies Reported 	Х	X			
Study/Epoch completion information		X			

x Assessment to be recorded in the clinical database or received electronically from a vendor

S- source documentation at the study site

 Visit structure given for internal programming purpose only

 Unless specified otherwise, assessments at 0 min should be done pre-dose

 Can be done at Day -1 instead of Day 1 if needed.

 Determined by QuantiFERON TB-Gold test

 Serum pregnancy test

 Urine pregnancy test

 Chemistry panel must be done under fasting conditions at all visits

 Only for patients who don't have an historical chest x-ray within 12 months from screening

 HRCT at screening should be performed after all other screening assessments for eligibility. A historical HRCT obtained within 12 months prior to screening may be used instead and sent to the central reader for analysis.

 Fasting glucose and [F]FDG-PET/CT must be done on a different day than the other assessments of V299 or after all other V299 assessments are completed on the same day.

 The [F]FDG-PET/CT requires a blood glucose level below 11 mmol/L. The measurement is performed by finger prick at site before [F]FDG-PET/CT is performed

 Clinical Status Determination includes the following: 6-minute walk distance, FVC, FEV1 and mMRC dyspnea score. Complete the form (found in the SOM) and use as a guide for CSE

 Discontinue methotrexate and azathioprine

 Patients with CSD of "deteriorating" will be ineligible to continue the study (during the run-in epoch); or they will increase steroid dose by 1-step (during the treatment epoch). See study design Section 3.1

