### 8.5.5 Steroid Titration

The Clinical Status Evaluation (CSE) serves as a safety evaluation and will serve to establish the patient's clinical status (Clinical Status Determination [CSD]) (Figure 3-2). CSE will be performed at visits (V102, V201, V202, V203, and V204) prior to the titration of steroids, and

Novartis	Confidential
Amended Protocol Version v08 (Clean)	

the CSD will guide selection of the next dose of steroids (Figure 3-3). Titration will continue throughout the run-in and treatment epochs. Patients with CSD of "improved" or "stable" will decrease steroid dose by 1-step on the dosing scale (Figure 3-4). Patients with CSD of "deteriorating" will be ineligible to continue the study (during the run-in epoch or at V201); or they will increase steroid dose by 1-step (during the treatment epoch).

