#### 11.4.2 Statistical model, hypothesis, and method of analysis

The change from baseline in percent predicted FVC will be analyzed using a Bayesian model for repeated measurements. The model will investigate effects for treatment by time (included as a class variable) interaction, baseline FVC by time interaction, prior sarcoidosis immunosuppressant therapy (stratification factor) and baseline prednisone dose. The correlation among the repeated measures collected on the same subject will be assessed via an unstructured covariance matrix. The stratification factor may be removed in case of strata with low sample sizes impacting on the convergence of the model.

Uninformative priors will be utilized to obtain the posterior estimates. Baseline is defined as Day 1.

The posterior probability that CMK389 is better than placebo in terms of change from baseline in percent predicted FVC at 16 weeks will be calculated. If it is at least 90%, it will be considered a sign of efficacy of CMK389 in this patient population.

The primary analysis will include all available data from patients in the PD analysis set with baseline and at least one post baseline assessment.

A supplementary analysis may be conducted including also FVC values collected after a change of the background therapy not based on the CSD algorithm.

Novartis	Confidential	Page 83
Amended Protocol Version v08 (Clean)		Protocol No. CCMK389X2201

If data permits, additional subgroup analysis of the primary endpoint will be conducted for the following three subgroups: increased, no change and decreased prednisone dose at week 16 compared to baseline.

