6.2 Secondary objectives

6.2.1 Variables

Secondary variables for this study are:

- Steroid use (mg days): Change from baseline in steroid usage as determined by the investigator's decision (for any reason algorithm mediated or just related to an investigator's decision).
- - Dose for subjects dosed with Methylprednisolone steroid doses of 4, 6, 8, 10 mg will be multiplied by 1.25 to become Prednisolone equivalent.
- Composite index of pulmonary physiology and exercise capacity: Subject who deteriorates from baseline to each visit/Week 16, is defined as a subject with:
 - o relative reduction if FVC \geq 10%, or
 - o relative reduction if FEV1 \geq 10%, or

- o relative reduction of DLCO \geq 15%, or
- o relative reduction of 6MWD \geq 50 m.
- [18F]FDG-PET/CT: Percent change from baseline in SUVmax and SUVmean
- Pulmonary function tests: Change from baseline in FVC (L), FEV1 (L and % predicted), FEV1/FVC, PEF and DLCO (absolute values and % predicted). DLCO expressed as % predicted and adjusted for Hemoglobin will be derived by the vendor as described in: Graham et others 2017. A composite physiological index (CPI) will be derived too following this formula: CPI = 91 0.65*DLCO(%) 0.53*FVC(%) + 0.34*FEV1(%)
- 6MWD: Change from baseline in distance walked and for the distance saturation product. The latter will be derived as the product between the distance walked and lowest oxygen saturation (SpO2%) value observed during the test, that is to say the lowest of the values taken after 1,2,3,4,5,6 Minutes from the start of the test (Lettieri 2006).
- IL-18 and IL-18bp concentrations

The direction of benefit is as follows

- an increase in values is beneficial for: absolute FVC, FEV1, PEF, DLCO and 6MWD.
- A decrease in values is beneficial for: [18F]FDG-PET/CT (SUVmax and SUVmean).

[18F]FDG-PET/CT

The [18F]FDG-PET/CT imaging data will be analyzed by the vendor to identify the standardized uptake values in the following categories:

- A maximum of 10 focal nodal uptake regions (mediastinal, hilar)
- A maximum of 10 focal regions of uptake in lung parenchyma
- A maximum of 10 extra-thoracic focal uptake regions on the whole body scan

[18F]FDG-PET/CT mean uptake in the reference tissue:

- Lung parenchyma, unaffected by focal lesion uptake
- Ascending aorta blood pool

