6.2.2 Descriptive analyses

All secondary variables will be listed by treatment, subject and visit/time. Descriptive statistics will be provided by treatment and visit/time for all continuous variables. Summary statistics will include arithmetic mean, SD, CV (arithmetic), median, minimum and maximum. Summary statistics for ancillary data (oxygen saturation, and vital signs data) collected during the 6 minute walking test will be provided too.

Il-18 and IL-18bp concentrations will be listed and summarized by treatment producing outputs mirroring the ones provided for the PK analysis of CMK389 concentrations but including the results observed in the placebo group.

Clinical status evaluation data (see section 3.1 of the study protocol) will be listed and summarized by treatment and visit. The summary table will report for each component (6MWT distance, FVC, FEV1, MMRC dyspnea score) the corresponding evaluation (Better, Same, Worse) and the overall evaluation.

Subjects who deteriorate at Weeks 4, 8, 12 and 16 and subjects with any increase in steroids for any reason (algorithm driven or not) during the treatment epoch will be summarized, separately, by treatment group using frequency tables.

The correlation between percent changes from baseline [18F]-FDG-PET/CT scan in SUVmax and changes from baseline in FVC, FEV1 and 6MWT distance will be assessed with scatterplot grids. As we may not be able to assume normality of the data, Kendall's tau-b coefficients and its corresponding p-values will be displayed to assess correlation.

Data on new lesions from [18F]-FDG-PET/CT will be only listed.

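### Two analyses of steroid dose need rework: treatment contrasts within final-dose groups are not randomised comparisons, and mg-days of steroid use has no modelled between-arm estimate (minor)

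*SAP*

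**What the plan says.** **Subgroups.** SAP 6.1.4 lists two groups, "subjects with a final prednisolone dose of 2.5 mg, subjects with a final prednisolone dose > 2.5 mg", and applies the primary model of SAP 6.1.3 within each, if data permit. Protocol 11.4.2 lists three: "increased, no change and decreased prednisone dose at week 16 compared to baseline". The SAP does not explain the change. SAP 6.2.3 allows the same subgroup analyses for the PET, lung-function and walk-distance endpoints if deemed necessary.

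**How the dose is set.** Protocol 8.5.5 states: "CSE will be performed at visits (V102, V201, V202, V203, and V204) prior to the titration of steroids". The resulting status guides the next dose. Protocol Table 8-1, footnote 12, gives the components: "Clinical Status Determination includes the following: 6-minute walk distance, FVC, FEV1 and mMRC dyspnea score". Under protocol 3.1, a patient who is improved or stable goes down one step, and a patient who deteriorates during the treatment epoch goes up one step. On Day 1 the step is taken first and randomisation follows.

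**Steroid use.** Protocol 2.2 makes steroid use in mg-days a secondary objective. SAP 6.2.1 defines the variable as "Steroid use (mg days): Change from baseline in steroid usage as determined by the investigator's decision", for any reason, and adds a methylprednisolone conversion. SAP 6.2.2 says: "Descriptive statistics will be provided by treatment and visit/time for all continuous variables". SAP 6.2.3 lists the continuous variables to be modelled, and steroid use is not among them. The only steroid outcome that it models is whether a patient had any dose increase, by logistic regression.

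**The concern.** A subgroup contrast keeps the protection of randomisation only if group membership is fixed before treatment can act on it. Final dose is not fixed in that way. It reflects starting dose, but also whether the patient deteriorated at V202, V203 or V204, and FVC is one of the items that decides this. If the drug prevents deteriorations, a placebo patient who still reaches 2.5 mg is a more selected patient than a treated one who does. Adjusting for baseline FVC and baseline prednisone does not remove that selection. The practical risk is that the estimate in the 2.5 mg group is read as the drug's effect at the lowest steroid dose.

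For mg-days, the issue is whether a stated secondary objective is answered. SAP 6.1 estimates the FVC effect irrespective of steroid dose. A reader therefore needs the between-arm difference in steroid exposure to interpret that effect: the same FVC gain means something different if one arm used more steroid. As written, the report could show mg-days by arm without an estimated difference, and under either of two definitions.

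**Working it through.** **1. The plan's own figure.** Protocol 11.7 gives 28 per arm, SD 9, true difference 5 and success if the posterior probability is at least 90% (one-sided 10% under uninformative priors).
- SE = 9 × √(2/28) = 2.41
- Power = Φ(5/2.41 − 1.28) = Φ(0.80) = 0.79, which agrees with the stated 80% or so.

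This figure is not disputed. If a dose group held half the patients (an assumption, 14 per arm), the SE would be 9 × √(2/14) = 3.40 and the power 0.57. The subgroup estimates would be imprecise even without bias.

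**2. Can conditioning on final dose distort the contrast?** The documents do not give the inputs, so this is an illustration only. Let FVC change be Y = δT + 9e, where T is 1 for active. Let a patient finish at 2.5 mg if rY/9 + bT + √(1 − r²)u > 0, with e and u independent standard normal. Here r is the correlation between the dose score and FVC change within an arm. The term b is any effect of treatment on dose by routes other than FVC, in SD units. Half of placebo finishes at 2.5 mg. Write λ(x) = φ(x)/Φ(x) and m = rδ/9 + b, with λ(0) = 0.798. The contrasts are then:
- 2.5 mg group: δ + 9r[λ(m) − λ(0)]
- > 2.5 mg group: δ − 9r[λ(−m) − λ(0)]

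Results:
- δ = 0, b = 0: m = 0, and both contrasts are exactly 0. There is no bias when treatment does not move dose.
- δ = 5, b = 0.5, r = 0.5: m = 0.778, λ(m) = 0.377, λ(−m) = 1.350. The contrasts are 5 + 4.5 × (0.377 − 0.798) = 3.1 and 5 − 4.5 × (1.350 − 0.798) = 2.5, although every patient's effect is 5.
- δ = 0, b = 0.5, r = 0.5: m = 0.5, λ(m) = 0.509, λ(−m) = 1.141. The contrasts are −1.3 and −1.5, although the drug does nothing to FVC.
- δ = 5 over r = 0.3 to 0.7 and b = 0 to 1: 1.0 to 4.7 in the 2.5 mg group and −1.6 to 4.7 in the > 2.5 mg group.

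A fuller simulation applied the status rule of protocol Figure 3-2, with assumed visit noise, starting doses and dose steps. For the same true effect of 5 it gave 3.6 to 5.0 (median 4.5) and 1.1 to 6.6 (median 5.1). The two models agree that bias is possible. They disagree on its size and, in the > 2.5 mg group, on its direction. Neither range should be taken as a prediction for this trial.

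**3. What mg-days could mean.** Assume 2.5 mg steps (the steps in protocol Figure 3-4 are not legible in the text available), four 28-day intervals (112 days) and a dose of 7.5 mg before the Day 1 step.

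| | Patient A: 5, 2.5, 2.5, 2.5 | Patient B: 5, 7.5, 5, 2.5 |
|---|---|---|
| Change in daily dose from 5 mg | −2.5 | −2.5 |
| Change in daily dose from 7.5 mg | −5 | −5 |
| Cumulative mg-days | 28 × 12.5 = 350 | 28 × 20 = 560 |
| Cumulative minus 112 × 5 | −210 | 0 |
| Cumulative minus 112 × 7.5 | −490 | −280 |

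A change in daily dose cannot tell these patients apart, while the total differs by 210 mg-days. The reference dose (before or after the Day 1 step) also changes the answer.

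**4. Why not divide by days observed.** If patient A left after the first interval, the observed average would be 5 mg/day, or 5 × 112 = 560 mg-days when scaled up, against 350 if the path had continued. Because doses usually fall over time, this rule overstates use in the arm with more early dropout.

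**The case against.** The strongest reply is that little rests on either analysis. The subgroup model is supportive, conditional on data, in a non-confirmatory proof-of-concept trial, and no decision rule uses it. The link from FVC to dose is also coarse. Improved and stable patients take the same downward step, so FVC acts only through the deteriorating category, which needs two worsened parameters or a rise of at least 2 mMRC points. All of this stands and is why the point is minor. It does not turn the contrast into a randomised one.

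On mg-days, by-arm summaries can satisfy the endpoint's literal wording. Protocol 11.5.1 also has a general sentence on modelling continuous variables collected at each treatment visit, which could be read to include steroid dose. It does not name it, and SAP 6.2.3 does not carry it over.

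A reader might infer more than the documents support:
- **That the primary estimate is biased.** It is not affected by this point, because the primary model does not condition on final dose.
- **That the trial has no modelled steroid comparison.** It has one, on any dose increase.
- **That mg-days was never given a formula.** None is visible in the protocol or SAP, but SAP 1.1 assigns derived-variable specifications to a separate document that was not available.
- **That the SAP dropped the 20% condition on the logistic model.** Protocol 11.5.1 states it, and the SAP says it implements the protocol, so silence does not revoke it.
- **That methylprednisolone doses outside the SAP's conversion list will be misclassified.** Such a dose would have to occur and also be left unconverted, and the specification may already cover it.

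**Conclusion.** Both parts hold, at minor severity.

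The within-group treatment contrasts of SAP 6.1.4, and those that the protocol 11.4.2 grouping would give, are not randomised comparisons. They are unbiased if treatment leaves the dose unchanged and can be biased otherwise. This follows from the titration rules alone. No figure for the bias can be defended, because it depends on how closely dose tracks FVC, on starting doses and on drug effects on the other status items, none of which the documents give.

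The mg-days objective lacks a modelled between-arm estimate in SAP 6.2.3, and its wording admits at least two readings that give materially different values. The 350 and 560 mg-days example rests on assumed 2.5 mg steps. The ambiguity itself does not.

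**What to change.** **Subgroups.** Tabulate the final-dose and dose-change groups by arm, with FVC summaries but no treatment-effect estimate. If a steroid subgroup model is wanted, define it by the assigned Day 1 prednisone-equivalent dose, which is set before randomisation. Use the same text in SAP 6.1.4 and protocol 11.4.2, and carry it through to the secondary endpoints in SAP 6.2.3.

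**Mg-days.** In SAP 6.2.1, define steroid use as cumulative actual prednisone-equivalent mg-days from Day 1 to V299, including increases outside the algorithm. In SAP 6.2.3, add one between-arm difference with its interval, adjusted for assigned Day 1 dose and for the immunosuppressant stratum. State a model-based method for patients who leave early, for example imputing their missing interval doses from arm, Day 1 dose and earlier doses. Do not divide by days observed.

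**Cost.** SAP wording, alignment with the protocol and one extra table from data that the CRF already collects. The inferential split by final dose is lost. The mg-days difference will be imprecise: simulations with 33 per arm and assumed dose paths gave an SE of 22 to 43 mg-days against true differences of 16 to 49 in size. It should be presented as an estimate and not as a test.

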6.1.5 Sensitivity/Supplementary analyses

Supplementary analyses may be conducted including also FVC values collected after a change of the background therapy driven by the algorithm or not.

Finally the analysis may be repeated excluding the observations with flags related to data quality (REIRESFL='Y').

A scatterplot will be produced to investigate the relationship between week 16 FVC changes from baseline and SUV max % changes

